4.2.4 Safety Population

The Safety population will comprise all randomized subjects receiving at least one dose of AVA and will be based on the actual treatment received, particularly, if this differs from that to which the subjects were randomized. That is, subjects randomized to receive both raxibacumab and AVA but only receive AVA will be summarized with the other subjects who only received AVA. Subjects in this population will be used for all safety summaries. Subjects who only receive raxibacumab will not be included in the safety population summaries.

Note: The Intent-to-Treat population and Per Protocol population will be analyzed as-randomized, rather than as-treated, in contrast to the Safety population.

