7.4. Safety

Clinical safety observations will include AEs, urinalysis, vital sign measurements, and clinical laboratory assessments. Planned time points for all safety assessments are listed in the Time and Events Table (Section 7.1). Additional time points for safety tests (such as vital signs, physical exams and laboratory safety tests) may be added during the course of the study based on newly available data to ensure appropriate safety monitoring.

Safety evaluations of data from clinical laboratory tests and spontaneous adverse event reporting will be performed for all subjects who receive study treatment. Details on specific safety assessments are provided below.

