9.3. Data Analysis Considerations

9.3.1. Analysis Populations

The Intent-to-Treat (ITT) population will comprise all randomized subjects.

The Per Protocol (PP) population will comprise all analyzable subjects and will be used for the primary analysis.

A subject will be considered to be analyzable if they meet all of the following criteria:

1. Receive at least the Week 0 and 2 AVA doses,

2. Receive the raxibacumab dose, if randomized to that treatment
3. Complete the primary study endpoint assessment (anti-PA Ab concentration at Week 4).

The Safety population will comprise all randomized subjects receiving at least one dose of study treatment and will be based on the actual treatment received if this differs from that to which the subjects were randomized. The Safety population will be the primary dataset used for the analysis of safety data. For analyses using the safety population only, subjects will be analyzed based on the treatment they received if this differs from the treatment to which they were randomized. That is, subjects randomized to receive both raxibacumab and AVA, who only receive AVA will be summarized with the other subjects who only received AVA. Subjects who only receive raxibacumab will not be included in the Safety population summaries and their data will be listed separately.

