9.4.2.3. Safety Analyses

Clinical safety observations will include AEs, urinalysis, vital sign measurements, and clinical laboratory assessments. Safety data will be tabulated and, where appropriate, analyzed by the use of descriptive statistics. Safety data will be tabulated for the Safety Population.

The number (%) of subjects withdrawing from the study will be summarized for each treatment group and the number (%) subjects withdrawing for each individual reason will be summarized by treatment group.

Reported AEs will be coded using MedDRA. The number (%) of subjects in each treatment group with treatment-emergent AEs will be compared for overall incidence and by system organ class and preferred term. Similar summaries will also be presented for deaths, all SAEs, AEs leading to withdrawal, and drug-related AEs. Severity of treatment-emergent AEs will also be summarized by system organ class, preferred term, and treatment group.

Additionally, the frequency of laboratory abnormality events along with shifts from baseline will be summarized, as well as changes over time in laboratory parameters, urinalysis and vital signs.

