All available data from subjects receiving at least 1 dose of AVA will be included in the safety analyses if valid. Extra measurements (such as unscheduled or repeat assessments) will not be included in the by-visit summary, but will be included in subject listings. All adverse events and clinical laboratory outliers that occur following the first dose of study medication will be included in the presentations of adverse events and outlier episodes, including episodes that occur at unscheduled evaluations.

Study disposition will be presented for All Subjects Enrolled population as defined in Section 4.2.1. Demographics will be presented for Intent-to-Treat population as defined in Section 4.2.2. Immunogenicity summaries will be presented for all subjects in the Per Protocol population as defined in Section 4.2.3. Safety summary statistics will be presented for all subjects in the Safety population as defined in Section 4.2.4. Data from subjects excluded from an analysis population will be included in the data listings, but not in the summaries.

Baseline, defined as the last scheduled observation prior to dosing, will correspond to Day -1 for clinical laboratory evaluations and vital signs and to Day 1, prior to administration of any study drug, for anti-PA Ab levels and TNA titers. Additionally, for subjects randomized to Treatment Group 2, baseline will correspond to Day 1, prior to administration of any study drug, for anti-raxibacumab Ab levels. However, if a subject is missing the baseline collection, the previous non-missing evaluation will become the baseline value. If no baseline or previous to baseline evaluations exist then the baseline value will be treated as missing.

In general, data will be presented by treatment (i.e., “AVA” and “Raxibacumab + AVA”). Data for all study subjects combined will also be presented when appropriate.

Some minor modifications may be necessary to the planned design of tables, figures, and listings to accommodate data collected during the actual study conduct.

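### Subjects who receive raxibacumab but no AVA enter no safety summary, so the adverse event tables can understate reactions to the infusion

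*SAP*

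**What the plan says.** SAP 4.2.4 defines the set by AVA: "The Safety population will comprise all randomized subjects receiving at least one dose of AVA". It uses that set for all safety summaries and then adds: "Subjects who only receive raxibacumab will not be included in the safety population summaries". SAP 4.1 is consistent with this. It says "All available data from subjects receiving at least 1 dose of AVA will be included in the safety analyses if valid", and of anyone outside an analysis set, "Data from subjects excluded from an analysis population will be included in the data listings, but not in the summaries".

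Protocol 9.3.1 opens more widely, with "The Safety population will comprise all randomized subjects receiving at least one dose of study treatment", but closes with an exception: "Subjects who only receive raxibacumab will not be included in the Safety population summaries and their data will be listed separately". Protocol 9.4.2.3 ties the tables to that set: "Safety data will be tabulated for the Safety Population". Protocol 7.4 speaks of a wider group: "Safety evaluations of data from clinical laboratory tests and spontaneous adverse event reporting will be performed for all subjects who receive study treatment".

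SAP 4.12.4.1 lists study treatment administration but summarizes it for AVA only (Days 1, 15 and 29). SAP 4.8 summarizes raxibacumab concentrations and PK parameters for Group 2.

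**The concern.** An exclusion from a safety table does little harm when it is unrelated to the events being counted. Here it can depend on them. Protocol 7.1 (Table 3) requires the infusion to be finished before the first AVA dose. Protocol 6.6 leaves vaccination after a hypersensitivity reaction to the investigator in consultation with the Medical Monitor. A subject who reacts to raxibacumab and is never vaccinated leaves both numerator and denominator of every adverse event table.

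This can happen only in Group 2, because a treated subject in the AVA-alone group has received AVA by definition. Infusion-related reactions are a named risk of raxibacumab in the risk table of protocol 4.6. At stake is the completeness of the tabulated safety description for that product, not the immunogenicity conclusion.

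**Working it through.** **1. The plan's own figure.** The documents give no infusion-reaction rate and no expected number of raxibacumab-only subjects, so there is no stated rate to reproduce. The sample size is used here only to set the size of Group 2. With margin log10(1.5) = 0.176, SD 0.75, one-sided 5% and a true ratio of 1, a fixed design needs 225 per arm. With the stated futility boundaries (1.0274, 0.4437, -1.645) at 30, 100 and 534 subjects, power is 79.99% against the stated 80%. So 534 subjects, 267 per group, reproduces.

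**2. Inputs.**
- Group 2 at full size: 267 analyzable (protocol 4.3), or about 620/2 = 310 if the estimated maximum is randomized.
- Group 2 at interim 1: 34/2 = 17 (34 randomized, SAP 2.5).
- Counts of reactors, and of reactors never given AVA: assumed.

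**3. Formula.** Let T be the number who started raxibacumab, x those with a reaction, and k those with a reaction who never receive AVA.
- Rate over all infused: x/T
- Rate shown in the tables: (x - k)/(T - k)
- Difference: x/T - (x - k)/(T - k) = k(T - x) / [T(T - k)]

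The difference is positive whenever k > 0 and x < T, so for infusion reactions the bias runs one way. If k = 0 it is nil.

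**4. Full trial, T = 267 (x and k assumed).**

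| x | x/T | shown, k = 1 | shown, k = 3 | shown, k = 5 |
|---|---|---|---|---|
| 5 | 1.9% | 4/266 = 1.5% | 2/264 = 0.8% | 0/262 = 0.0% |
| 13 | 4.9% | 12/266 = 4.5% | 10/264 = 3.8% | 8/262 = 3.1% |
| 27 | 10.1% | 26/266 = 9.8% | 24/264 = 9.1% | 22/262 = 8.4% |

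Taking T = 267 is a simplification: all 267 analyzable subjects in Group 2 have had AVA, so any raxibacumab-only subjects come on top. At T = 310 with x = 13, 13/310 = 4.2% would be shown as 12/309 = 3.9% (k = 1) to 8/305 = 2.6% (k = 5), much the same picture.

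**5. Early stop.** At interim 1, with T = 17 and x = k = 1, 1/17 = 5.9% is shown as 0/16 = 0%. At interim 2, one such subject in addition to 50 vaccinated (100/2) turns 1/51 = 2.0% into 0/50.

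**6. Other events.** The direction depends on the event. If 3 raxibacumab-only subjects lack an event shown at 50% among 267, the rate over all infused is 0.5 × 267/270 = 49.4%, so leaving them out slightly raises that rate.

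**7. Can the rate be recovered elsewhere?**
- Listings (SAP 4.1, 4.12.4.2; protocol 9.3.1) give cases without a denominator.
- Disposition (SAP 4.5) gives reasons for discontinuation, not infusions started or stopped.
- The Safety Review Team sees aggregate blinded data (protocol 6.3).
- The number of PK samples just after infusion approximates the number infused, subject to missed samples, but is not paired with an event count.

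None of these yields a reaction rate over all infused subjects.

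**The case against.** The exclusion is deliberate and prespecified in both documents, and it fits the stated safety objective, which compares AVA given with raxibacumab against AVA alone. That stands, and it is why the AVA-based set should remain for that comparison.

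The affected group may be very small. Protocol 6.6 describes the reactions as mild and successfully prevented by an antihistamine. AVA is not barred after a reaction, and a later AVA dose brings the subject back into the tables. No infusion-reaction rate is a planned endpoint; a reader would derive it from the tables of treatment-emergent events. All of this stands and limits the size of the point.

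Four stronger readings are tempting, but the documents do not support them:

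- **That raxibacumab exposure goes unsummarized.** Concentrations and PK parameters are summarized. Only the count of doses given, complete or interrupted, is missing from the summaries.
- **That protocol and SAP contradict each other on who is tabulated.** Protocol 9.3.1 can be read as a general rule with an express exception, which the SAP builds into its definition. The subjects summarized are then the same, and SAP 4.13 has no change of analysis to record. Protocol 7.4 asks for evaluation, not tabulation.
- **That the events are lost or unseen.** They are listed. Independent unblinded statistical and medical personnel receive listings of adverse events, serious events and withdrawals due to events at each interim (SAP 4.9), and treatment may be unblinded for any serious event (protocol 6.3).
- **That the tables would show no reactions at all.** At full size this requires every reactor to miss AVA, which is an extreme assumption.

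In the other direction, SAP 4.1 also says that all adverse events after the first dose of study medication will be presented. This does not settle the matter: a presentation may be a listing, and the specific sentence in SAP 4.2.4 governs the summaries.

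**Conclusion.** The point holds as a modest reporting gap. As written, a reaction to raxibacumab can cause a Group 2 subject to be left out of every adverse event summary, and no planned output gives the rate over all infused subjects. Across the scenarios tabulated at 267 infused, the understatement is about 0.3 to 1.9 percentage points. After a stop at interim 1, one subject moves the rate by about 6 points. These sizes rest wholly on assumed counts of reactors and of reactors never given AVA, and the effect is zero if every infused subject receives AVA.

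The reading of the text is firm; the practical impact is unknown and probably small. The primary and futility analyses use the per-protocol set, whose members have all received AVA, and are unaffected. The case for acting rests on the low cost and on the exclusion being linked to the outcome, not on any expected large bias.

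**What to change.** - Keep the AVA-based Safety population for the comparison of AVA with raxibacumab + AVA.
- In SAP 4.12.4.2, add a supplementary summary of treatment-emergent events, including infusion-related reactions, in all subjects who started a raxibacumab infusion, whether or not they received AVA.
- In SAP 4.12.4.1, add the number (%) of subjects whose raxibacumab infusion was started, completed, and interrupted or stopped.
- As tidy-up, align the opening sentence of protocol 9.3.1 with its own exclusion sentence and with SAP 4.2.4.

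The cost is one extra table, one exposure row and a small wording change in the protocol. With few affected subjects the table partly repeats the listing; the gain is a denominator of all infused subjects. Administration is already listed, but the documents do not say whether an interrupted infusion is flagged in the CRF, so that should be checked. The change alters no clinical rule and leaves the comparison of arms as planned.

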4.3 Incomplete and Missing Data

For safety summaries, no adjustment or imputation will be utilized for missing values or for subjects who withdraw prior to completing the study. Also, no analyses will be restricted to subjects with complete data.

4.4 Protocol Deviations

All protocol deviations will be tracked by the study team throughout the conduct of the study in accordance with the PDMP. See Appendix I of PDMP for a list of protocol deviations that are considered important. Data will be reviewed prior to unblinding and freezing the database to ensure all important deviations and deviations which may lead to exclusion from the analysis populations are captured and categorized on the protocol deviations dataset. This dataset will be the basis for the summaries and listings of protocol deviations, as well as the definition of the Per Protocol population.

- Important protocol deviations (including deviations related to study inclusion/exclusion criteria, conduct of the trial, patient management or patient assessment) will be summarized by category and listed.

- Important deviations which result in exclusion from the analysis population will also be summarized by category and listed.

4.5 Subject Disposition

A subject will be considered enrolled at the time of providing informed consent. Subjects will be considered to have completed the study if they have completed all study visits including the follow-up visit.

Subject accountability will be tabulated by treatment and for all subjects overall by summarizing the number of subjects who enrolled (i.e., provide the informed consent), are randomly assigned to treatment, complete the study, or prematurely discontinue along with the reason for early discontinuation. A listing will be presented to describe dates of completion or early withdrawal and the reason for early discontinuation, if applicable, for each subject.

Listings of study eligibility, treatment randomization, and study treatment administration will be provided.

4.6 Demographic and Baseline Characteristics

Individual subject demographics and baseline characteristics (medical history and results from urine drug and alcohol screens, serology screening, and pregnancy tests) will be presented in listings.

Demographic characteristics such as age, sex, race, ethnicity, height, weight, and body mass index (BMI) will be summarized and tabulated by treatment and for all subjects overall. Descriptive statistics will be presented for age, height, weight, and BMI. Frequency counts and percents will be presented for sex, race, and ethnicity.

4.7 Previous and Concomitant Medications

Previous medications are defined as any medication discontinued prior to the first dose of study drug. Concomitant medications are defined as any medication taken during the course of the study. A subject listing and a summary of all previous and concomitant medications will be presented. All medications will be coded and classified by anatomic-therapeutic-chemical classification (ATC) Level 1 Code using the GSK Drug System.

See Appendix A for handling of partial dates for medications. In the case where it is not possible to define a medication as prior, concomitant, or post-treatment, the medication will be classified as concomitant.

4.8 Pharmacokinetic Analyses

A listing of PK blood sample collection times as well as derived sampling time deviations will be provided.

Drug concentration-time data will be listed for each subject in Treatment Group 2 and summarized by descriptive statistics at each nominal collection time. Below the limit of quantitation (BLQ) concentrations will be treated as zero for computation of descriptive statistics. Concentrations assigned a value of missing will be omitted from the calculation of descriptive statistics. If the calculated mean concentration is BLQ, the mean value will be reported as BLQ. SD will be reported as ND (not determined). Minimum, median, and maximum may be reported. If any of these values are BLQ, they will be reported as such and indicated as BLQ.

Figures of mean raxibacumab concentration-time data in Treatment Group 2 will be presented on linear and semi-logarithmic scales. Individual subject concentration-time data will be graphically presented on linear and semi-logarithmic scales.

Predose samples that are BLQ or missing will be assigned a numerical value of zero for the calculation of area under the concentration-time curve (AUC). Predose samples that are missing will be excluded from the concentration summary calculations. Any anomalous concentration values observed at predose will be identified in the study report and used for the computation of AUC. Pharmacokinetic parameters will be computed and reported if the anomalous value is not greater than 5% of the observed maximum concentration (C_{max}). If the anomalous value is greater than 5% of C_{max} , the PK parameters for the given subject will be computed in the PK analysis but will not be reported.

Any other BLQ concentrations that precede quantifiable samples in the initial portion of the profile or a BLQ value that occurs between quantifiable data points, especially prior to C_{max} , will be evaluated to determine if an assigned concentration of zero makes sense, or if reanalysis or exclusion of the data is warranted. Following C_{max} , BLQ values embedded between 2 quantifiable data points will be treated as missing when calculating AUC. If BLQ values occur at the end of the collection interval (after the last quantifiable concentration), these will be treated as missing data. If consecutive BLQ concentrations are followed by quantifiable concentrations in the terminal portion of the concentration curve, these quantified values will be excluded from the PK analysis by assigning them a value of missing, unless otherwise warranted by the concentration-time profile.

Specimens will also be analyzed for the presence of anti-raxibacumab antibodies. Those results will be descriptively and/or graphically summarized as appropriate to the data.

The following plasma PK parameters will be estimated by noncompartmental methods for serum raxibacumab if data permits:

C_{\max}	Maximum observed serum raxibacumab concentration.
t_{\max}	Time of occurrence for C_{\max} .
AUC_{0-t}	Area under the serum raxibacumab concentration-time curve to the time of the last measurable concentration.
$AUC_{0-\infty}$	Area under the serum raxibacumab concentration-time curve to infinite time.
λ_z	Terminal elimination rate constant.
$t_{1/2,z}$	Half-life of drug elimination in the terminal phase.
MRT	Mean residence time.
CL	Clearance.
V_z	Volume of distribution in the terminal phase.
V_{ss}	Volume of distribution at steady-state.

The following PK parameters will be calculated for diagnostic purposes and listed, but will not be summarized:

$t_{1/2, \text{Interval}}$	The time interval (days) of the log-linear regression to determine $t_{1/2}$
$t_{1/2,N}$	Number of data points included in the log-linear regression analysis
Rsq	Goodness of fit statistic for calculation of λ_z (Regression coefficient). If Rsq is less than 0.800, λ_z and related parameters will not be reported.
$\%AUC_{\text{ex}}$	Percentage of $AUC_{0-\infty}$ obtained by extrapolation, calculated as $[(C_{\text{last}}/\lambda_z)/AUC_{0-\infty} * 100]$

A subject listing of individual PK parameters will be provided. Pharmacokinetic parameters will be summarized using descriptive statistics. For t_{\max} only mean, minimum, maximum and median will be reported.

4.9 Interim Analyses

Two interim analyses are scheduled to allow early termination of the study if a large effect of raxibacumab on AVA immunogenicity is confirmed at the interim. The first interim analysis will be performed after at least 30 analyzable subjects have reached the Week 4 endpoint. The trial is randomizing 34 patients to ensure that at least 30 subjects are analyzable, so it is possible that there will be more than 30 patients analyzed in the first interim. The second interim will be performed after the first 100 analyzable subjects have reached the Week 4 endpoint. There may also be additional subjects randomized to meet the total of 100 analyzable subjects for the second interim. The final number enrolled will be informed by the level of drop-outs observed in the first 34 subjects randomized.

These interim analyses will be performed on the per-protocol population by independent unblinded statistical and medical personnel using unblinded data.

For the interim analyses, the immunogenicity data will be summarized by the ratio of geometric mean concentrations (GMC) of anti-PA antibody levels with corresponding 95% CI. A two sample t-test for the log transformed data will be performed and a corresponding p-value will be provided which will be used to determine if the futility threshold has been crossed at the respective interim analyses. No imputations will be utilized for interim analyses. The study will be terminated early if the futility boundary is crossed at an interim, otherwise, recruitment for next phase will begin.

The futility thresholds for the interim analyses will be based on a rho (0.5) type II error spending function. The t-statistics for the boundaries, as calculated in East 5.4, are 1.0274 for interim 1 (sample size = 30 subjects), 0.4437 for interim 2 (sample size = 100 subjects) and -1.645 for the final analysis. These correspond to p-values for the t-test of p=0.848 at interim 1, p=0.671 at interim 2, and p=0.05 for the final analysis.

Note: The futility boundary will be recalculated by the unblinded statistician based on the actual number of subjects who comprise the primary analysis population for cohort 1. These boundaries will be calculated using East 6.2.

For these interim analyses, the results will include:

- calculations of futility boundaries (Table 14.2.3.1.1);
- a summary of statistical comparison of anti-PA antibody levels (Table 14.2.3.1.2);
- a demographic summary (Table 14.1.2);
- a listing and a summary of the observed AEs (Listing 16.2.7.2, Table 14.3.1.2);
- a listing of serious AEs (Listing 14.3.2.2);

- a listing of AEs leading to withdrawal from study (Listing 14.3.2.3);
- a listing and a summary of laboratory assessments (Listing 16.2.8.1.1, Table 14.3.6.1, Table 14.3.6.2); and
- a listing and a summary of vital signs (Listing 16.2.8.2.1, Table 14.3.6.5, Table 14.3.6.6).

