The t-statistics for the boundaries, as calculated in East 5.4, are 1.0274 for interim 1, 0.4437 for interim 2 and -1.645 for the final analysis. These correspond to p-values for the t-test of $p=.848$ at interim 1, $p=.671$ at interim 2, and $p=.05$ for the final analysis.

The clinical interpretation of these thresholds is easier to evaluate if they are converted to thresholds for the GMC ratio. The challenge with this conversion is that the thresholds for the GMC ratios that will lead to a futility result or a result of non-inferiority will be dependent on the variability in the estimates observed in the trial. However, a conversion can be made assuming the standard deviation will match the one used in the sample size calculation of 0.75. Under this assumption, the log transformed scale the boundaries correspond approximately to an observed difference in the means of $>.4575$ at interim 1 and $>.242$ at interim 2, or observed GMC ratios of > 2.87 and >1.75 respectively. The threshold for success at the final analysis would be an observed GMC ratio of 1.173 or less.

Given the high level of variance of anti-PA antibody levels at week 4 with AVA (as observed in [Marano, 2008](#)), it is challenging to estimate either the GMC or the GMC ratios with precision without a very large sample size. The total sample size was determined based on how many subjects were required to have an 80% chance of ruling out that the GMC ratio was >1.5 when it was truly 1. Many more subjects would be required to estimate the actual ratio with considerable precision.

Similarly the interim analyses will not result in precise estimates of the GMC ratio. There will be sufficient data collected to determine whether it is futile to expect that the trial would result in a non-inferiority conclusion. The beta error spending boundary was chosen such that approximately 25% of the Type II error is spent in the first interim. There was a willingness to allow for this much error in the first interim after only 30 subjects, because it is assumed that there is a high likelihood the anti-PA antibody levels will be inferior when raxibacumab is given with AVA, based on the results of the [Malkevich \(2013\)](#) paper.

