At the first interim the confidence interval for the ratio will be based on a t statistic with 28 degrees of freedom (for instance for a 90% CI the relevant t value is $t_{.05,28}=1.701$). The exact precision of the estimate will be dependent on the observed sample estimate of the standard deviations. Assuming both treatment groups have a sample standard deviation equivalent to the assumed 0.75, the assumed standard error would be 0.274. The 90% confidence interval will vary by $\pm .466$. Translated back to the original scale, the GMC ratio will be scaled by .342 or 2.92.

For the second interim, the assumed standard error in the log transformed data would be .15. The 90% confidence interval would vary by $\pm .249$ in the log transformed data and scaled 0.564 or 1.775 in the original scale GMC ratio.

At the final analysis, the assumed standard error in the log transformed data would be .065. The 90% confidence interval would vary by $\pm .107$ in the log transformed data and scaled by 0.782 or 1.28 in the original scale GMC ratio.

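### At interim 1 the printed futility boundary t = 1.0274 and the p-value 0.848 said to match it are not the same rule on 28 degrees of freedom

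*SAP*

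**What the plan says.** SAP 4.9 specifies a two-sample t-test on the log-transformed data at each interim and makes its p-value the decision quantity: "a corresponding p-value will be provided which will be used to determine if the futility threshold has been crossed at the respective interim analyses". It then lists the boundaries as t-statistics, which "are 1.0274 for interim 1 (sample size = 30 subjects), 0.4437 for interim 2 (sample size = 100 subjects"), with −1.645 at the final analysis, and pairs them with p-values: "These correspond to p-values for the t-test of p=0.848 at interim 1", followed by 0.671 at interim 2 and 0.05 at the final analysis.

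Protocol 9.3.2 gives the same pairs: "The t-statistics for the boundaries, as calculated in East 5.4, are 1.0274 for interim 1, 0.4437 for interim 2". Assuming an SD of 0.75, it converts the two interim boundaries to differences on the log10 scale and then to ratios: "or observed GMC ratios of > 2.87 and >1.75 respectively". On the reference distribution it says: "At the first interim the confidence interval for the ratio will be based on a t statistic with 28 degrees of freedom".

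The null value is given elsewhere in the SAP. Section 2.4 states the margin as log10(1.5) = 0.176, and section 4.10 states the null hypothesis as a GMC ratio of at least 1.5. Section 4.9 itself gives neither the formula for the statistic nor the direction of the p-value.

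SAP 4.9 also says that the futility boundary will be recalculated in East 6.2 for the number of subjects actually analysed in cohort 1. It does not say on which scale, or against which reference distribution, the new boundary will be expressed.

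**The concern.** The t boundary and its p-value are presented as two expressions of one rule. With 15 subjects per arm the t and normal distributions still differ in the third decimal place. A boundary on the normal scale and the p-value of a t-test are therefore not interchangeable at the printed precision.

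If the two figures are different rules, there is a band of results in which the unblinded statistician would stop by one and continue by the other. The rule decides whether a trial planned for 534 analyzable subjects ends after about 30, so it should have only one reading.

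**Working it through.** **Inputs.** n = 30 with 1:1 allocation, and SD 0.75 on the log10 scale (SAP 2.4). Margin log10(1.5) = 0.1761 (SAP 2.4, 4.10). Boundaries 1.0274, 0.4437 and −1.645 with p-values 0.848, 0.671 and 0.05 (SAP 4.9, protocol 9.3.2). Degrees of freedom at interim 1: 28 (protocol 9.3.2). Type II error 20%, rho spending with rho = 0.5 (SAP 2.4).

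**Step 1: reproduce the design.** Cumulative type II spending at interim 1 is 0.2 × (30/534)^0.5 = 0.0474. Joint normal integration over looks at 30, 100 and 534 with the stated boundaries gives a stopping probability of 0.0474 at interim 1 when the true ratio is 1, and overall power of 0.7999. The boundaries and the sample size reproduce, with 1.0274 treated as a normal-scale boundary.

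**Step 2: reproduce the ratio cut-off.** SE = 0.75 × √(2/15) = 0.2739. The difference at the boundary is 0.1761 + 1.0274 × 0.2739 = 0.4575, and 10^0.4575 = 2.87, as protocol 9.3.2 states. This confirms that the intended statistic is centred on log10(1.5).

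**Step 3: convert each boundary to a lower-tail probability.**

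| Look | Boundary | Normal | t, n−2 df | Printed p |
|---|---|---|---|---|
| Interim 1 (28 df) | 1.0274 | 0.8479 | 0.8435 | 0.848 |
| Interim 2 (98 df) | 0.4437 | 0.6714 | 0.6709 | 0.671 |
| Final (532 df) | −1.645 | 0.0500 | 0.0503 | 0.05 |

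Only interim 1 conflicts. The printed 0.848 is the normal value.

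**Step 4: invert the printed p-value.** On 28 df, p = 0.848 corresponds to t = 1.047 (1.045 to 1.049 over the rounding of 0.848). The difference is 0.1761 + 1.0471 × 0.2739 = 0.4629, a ratio of 2.90.

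**Step 5: size of the disagreement.** Probability of stopping at interim 1 from the noncentral t on 28 df, SD 0.75:

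| True ratio | Stop if t > 1.0274 | Stop if p > 0.848 | Difference (points) |
|---|---|---|---|
| 1 | 4.99% | 4.80% | 0.19 |
| 1.5 | 15.65% | 15.20% | 0.45 |
| 2 | 28.88% | 28.23% | 0.65 |
| 4 | 70.27% | 69.59% | 0.68 |
| 10 | 97.57% | 97.45% | 0.12 |

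Between the tabulated ratios the difference peaks at about 0.77 points, near a true ratio of 2.9. In a simulation of 40,000 trials at ratio 1, power was 79.99% under the t rule and 79.95% under the p rule, so the choice does not matter for power.

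**Step 6: recalculation.** As an illustration, if all 34 subjects randomized in cohort 1 were analyzable and the boundary stayed at 1.0274, the t-test probability on 32 df would be 0.844, still not 0.848. Recalculating for n does not by itself settle which scale governs.

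**The case against.** The strongest reply is that the SAP already names one operative rule, the p-value, so only a label is wrong: a normal-scale boundary has been called a t-statistic. Taking the nominal p-value from a normal-theory boundary and applying it to the t-test p-value is a coherent small-sample practice. At ratio 1 it stops 4.80% of trials, closer to the planned spending of 4.74% than the 4.99% under the t rule. This stands, and it is a reason not to insist that the t boundary must govern. It does not remove the mismatch, because the same section prints 1.0274 as the t boundary and the protocol's 2.87 is derived from it.

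A reader might infer from protocol Table 5, which prints 15.8% stopping at interim 1 for ratio 1.5, that the t rule is the intended one. That row does not settle it. Stopping at interim 1 for ratio 1.5 does not depend on the SD, and Table 6 prints 15.1% for the same ratio. The exact values are 15.65% (t rule) and 15.20% (p rule), and the Monte Carlo standard error with 10,000 trials is √(0.152 × 0.848/10,000) = 0.36 points.

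A reader might also infer that, because SAP 4.9 describes only a two-sample t-test, the interim test will be run against no difference. That would lower the limits to observed ratios of 1.91 and 1.17, raise futility stopping at ratio 1 to about 38% and cut power to about 57%. The documents do not support this reading. SAP 2.4 gives the margin, SAP 4.10 gives the null hypothesis as a ratio of at least 1.5, and the boundary series in SAP 4.9 ends at −1.645 with p = 0.05, which is the final non-inferiority test. The protocol's 2.87 and 1.75 fit only a centred statistic. The figures show why the centring is worth writing into 4.9. They do not describe the plan read as a whole.

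Finally, the n = 30 figures may be superseded by the planned recalculation. That is true, but the recalculation note leaves the scale open.

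**Conclusion.** The point holds as a small but real inconsistency in a stop/continue threshold. At interim 1, t = 1.0274 and a t-test p-value of 0.848 do not correspond on 28 df. The matching pairs are 1.0274 with 0.8435 (ratio 2.87) and 1.047 with 0.848 (ratio 2.90). The two rules disagree only when the statistic falls between 1.027 and 1.047. That changes interim 1 stopping by about 0.7 percentage points at most at the Table 5 ratios (under 0.8 at any ratio) and leaves power essentially unchanged. Interim 2 and the final analysis are unaffected at the printed precision.

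The sizes assume 15 analyzable subjects per arm, normal log10 data with a common SD of 0.75, and a pooled-variance statistic centred on log10(1.5). The 28 df mismatch between t and p does not depend on the SD; the ratio cut-offs do. The documents do not establish which of the two rules was meant to govern, and either is defensible.

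**What to change.** In SAP 4.9, define the interim statistic as T = [mean log10(AVA) − mean log10(AVA + raxibacumab) − log10(1.5)] / pooled SE, with n−2 degrees of freedom. State that the test is one-sided, that the p-value is P(T(n−2) ≤ observed T), and that the trial stops if the boundary is exceeded. This agrees with SAP 2.4 and 4.10.

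Name one decisive scale and make the interim 1 figures agree:

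- **t rule:** t = 1.0274, p = 0.8435, observed ratio 2.87 at SD 0.75. This keeps the protocol's converted cut-off.
- **p rule:** p = 0.848, t = 1.047, observed ratio 2.90 at SD 0.75, with 1.0274 labelled as a z-scale boundary. This keeps the decision quantity that the SAP names and lies closer to the planned type II spending.

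Print the ratio equivalents in the SAP as a check (1.75 at interim 2 under either rule). State that the same convention applies when the boundary is recalculated for the actual n, and correct protocol 9.3.2 to match. Settle the choice before the first unblinded look.

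The cost is a few sentences and up to three figures in two documents. No change to data collection, sample size or design is needed.
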